7.2. Screening and Critical Baseline Assessments

Cardiovascular medical history/risk factors (as detailed in the CRF) will be assessed at screening.

The following demographic parameters will be captured: year of birth, sex, race and ethnicity.

Medical/medication/family history will be assessed as related to the inclusion/exclusion criteria listed in Section 5.

Procedures conducted as part of the participant's routine clinical management and obtained prior to signing of informed consent may be utilised for screening or baseline purposes provided the procedure meets the protocol-defined criteria and has been performed within the timeframe defined in the Time and Events Schedule.

The Asthma Control Test ([Appendix 7](#)) should be completed by participants before any other assessment at a clinic visit, in the order specified.

7.3. Safety

Planned time points for all safety assessments are listed in the Time and Events Table (Section 7.1). Additional time points for safety tests (such as vital signs, physical exams and laboratory safety tests) may be added during the course of the study based on newly available data to ensure appropriate safety monitoring.

7.3.1. Adverse Events (AE) and Serious Adverse Events (SAEs)

The definitions of an AE or SAE can be found in [Appendix 5](#).

The investigator and their designees are responsible for detecting, documenting and reporting events that meet the definition of an AE or SAE.

7.3.1.1. Time period and Frequency for collecting AE and SAE information

- Any SAEs assessed as related to study participation (e.g., protocol-mandated procedures, invasive tests, or change in existing therapy) or related to a GSK product will be recorded from the time a participant consents to participate in the study up to dosing, and all SAEs will be documented after dosing, including any follow-up contact.
- AEs will be collected from the start of Study Treatment until the follow-up contact (see Section 7.3.1.3), at the time points specified in the Time and Events Table (Section 7.1).
- Medical occurrences that begin prior to the start of study treatment but after obtaining informed consent may be recorded on the Medical History/Current Medical Conditions section of the CRF.
- All SAEs will be recorded and reported to GSK within 24 hours, as indicated in [Appendix 5](#).

- Investigators are not obligated to actively seek AEs or SAEs in former study participants. However, if the investigator learns of any SAE, including a death, at any time after a participant has been discharged from the study, and he/she considers the event reasonably related to the study treatment or study participation, the investigator must promptly notify GSK.

NOTE: The method of recording, evaluating and assessing causality of AEs and SAEs plus procedures for completing and transmitting SAE reports to GSK are provided in [Appendix 5](#).

7.3.1.2. Method of Detecting AEs and SAEs

Care will be taken not to introduce bias when detecting AEs and/or SAEs. Open-ended and non-leading verbal questioning of the participant is the preferred method to inquire about AE occurrence. Appropriate questions include:

- “How are you feeling?”
- “Have you had any (other) medical problems since your last visit/contact?”
- “Have you taken any new medicines, other than those provided in this study, since your last visit/contact?”

7.3.1.3. Follow-up of AEs and SAEs

After the initial AE/SAE report, the investigator is required to proactively follow each participant at subsequent visits/contacts. All AEs will be followed until resolution, until the condition stabilises, until the event is otherwise explained, or until the participant is lost to follow-up (as defined in Section [5.4](#)). Further information on follow-up procedures is given in [Appendix 5](#).

7.3.1.4. Cardiovascular and Death Events

For any CV events detailed in [Appendix 5](#) and all deaths, whether or not they are considered SAEs, specific CV and Death sections of the CRF will be required to be completed. These sections include questions regarding cardiovascular (including sudden cardiac death) and non-cardiovascular death.

The CV CRFs are presented as queries in response to reporting of certain CV Medical Dictionary for Regulatory Activities (MedDRA) terms. The CV information should be recorded in the specific cardiovascular section of the CRF within one week of receipt of a CV Event data query prompting its completion.

The Death CRF is provided immediately after the occurrence or outcome of death is reported. Initial and follow-up reports regarding death must be completed within one week of when the death is reported.

7.3.1.5. Regulatory Reporting Requirements for SAEs

Prompt notification by the investigator to GSK of SAEs related to study treatment (even for non- interventional post-marketing studies) is essential so that legal obligations and

ethical responsibilities towards the safety of participants and the safety of a product under clinical investigation are met.

GSK has a legal responsibility to notify both the local regulatory authority and other regulatory agencies about the safety of a product under clinical investigation. GSK will comply with country specific regulatory requirements relating to safety reporting to the regulatory authority, IRB/ IEC and investigators.

Investigator safety reports are prepared for suspected unexpected serious adverse reactions according to local regulatory requirements and GSK policy and are forwarded to investigators as necessary.

An investigator who receives an investigator safety report describing a SAE(s) or other specific safety information (e.g., summary or listing of SAEs) from GSK will file it with the IB and will notify the IRB/IEC, if appropriate according to local requirements.

7.3.2. Pregnancy

Only women of non-childbearing potential are eligible for this study, so pregnancies are not expected. However, if a pregnancy does occur then: details of all pregnancies in females will be collected after the start of dosing and until the end of the mandated contraceptive period. If a pregnancy is reported then the investigator should inform GSK within 2 weeks of learning of the pregnancy and should follow the procedures outlined in [Appendix 6](#).

7.3.3. Physical Exams

- A complete physical examination will include, at a minimum, assessment of the Skin, Eyes and Cardiovascular, Respiratory, Gastrointestinal and Neurological systems. Height (screening only) and weight will also be measured and recorded.
- A brief physical examination will include, at a minimum, assessments of the skin, lungs, cardiovascular system, and abdomen (liver and spleen).
- Investigators should pay special attention to clinical signs related to previous serious illnesses

7.3.4. Vital Signs

- Vital signs will be measured in supine position after 5 minutes rest and will include temperature, systolic and diastolic blood pressure, heart rate and respiratory rate.

7.3.5. Electrocardiogram (ECG)

- 12-lead ECGs will be obtained using an ECG machine that automatically calculates the heart rate and measures PR, QRS, QT, and QTc intervals. Refer to Section [5.4.3.2](#) for QTc increased monitoring criteria and additional QTc readings that may be necessary.

The 12-lead ECG will be performed in the supine position. At all time points, after a 5 minutes rest, triplicate ECGs will be obtained over a brief recording period (up to

10 minutes). The ECGs will be time-matched to baseline assessment (ie pre-dose on Day 1) from Day 2 onwards. For QT interval corrected for heart rate (QTc), for the purposes of standardisation, Fridericia's correction formula (QTcF) was selected and will be used across sites with central over-read to limit variability.

7.3.6. Clinical Safety Laboratory Assessments

All protocol required laboratory assessments, as defined in [Table 5](#), must be conducted in accordance with the Laboratory Manual, and Protocol Time and Events Schedule.

Laboratory requisition forms must be completed and samples must be clearly labelled with the participant number, protocol number, site/centre number, and visit date. Details for the preparation and shipment of samples will be provided by the laboratory and are detailed in the SRM. Reference ranges for all safety parameters will be provided to the site by the laboratory responsible for the assessments.

If additional, non-protocol specified, laboratory assessments are performed at the institution's local laboratory and result in a change in participant management or are considered clinically significant by the investigator (e.g., SAE or AE or dose modification) the results must be recorded in the CRF.

Refer to the SRM for appropriate processing and handling of samples to avoid duplicate and/or additional blood draws.

All study-required laboratory assessments will be performed by a central laboratory, except for pre-screen eosinophils, which, if required, may be performed at the local laboratory.

NOTE: Local laboratory results are only required in the event that the central laboratory results are not available in time for either a treatment and/or response evaluation to be performed – for example: on Day –1, when results should be available before dosing on Day 1; at 48 h post-dose for all sentinel participants; at 48 h post-dose when results should be available before the participant is discharged from the clinical unit in the UK; on Day 8, when results should be available before the participant is discharged from the clinical unit in Germany; or at any other time when a participant is unwell and results are required urgently. If a local sample is required it is important that the sample for central analysis is obtained at the same time. Additionally, if the local laboratory results are used to make either a treatment or response evaluation, the results must be entered into the CRF.

Haematology, clinical chemistry, urinalysis and additional parameters to be tested are listed in [Table 5](#).

Table 5 Protocol Required Safety Laboratory Assessments

Laboratory Assessments	Parameters				
Haematology	Platelet Count		RBC Indices:	WBC count with Differential: (post-dose results blinded as described in footnote 1)	
	RBC Count		MCV	WBC	
				Neutrophils	
	Haemoglobin		MCH	Lymphocytes	
	Haematocrit			Monocytes	
				Eosinophils	
				Basophils	
Clinical Chemistry	BUN	Potassium	AST (SGOT)		
	Creatinine	Sodium	ALT (SGPT)		
	Glucose (fasted at screening)	Calcium	Alkaline phosphatase	Albumin	
		Magnesium			
Routine Urinalysis	
 Specific gravity pH, glucose, protein, blood and ketones by dipstick Microscopic examination and UACR (if blood or protein is abnormal [evidence of microalbuminuria or haematuria of $\geq 1+$]) 				
Other tests	
 hsCRP 				
Other Screening Tests	
 HIV Hepatitis B (HBsAg; in Germany only, anti-HBc will also be tested [Appendix 8]) Hepatitis C (Hep C antibody) FSH and estradiol (if required to confirm postmenopausal status) Alcohol, cotinine and drug screen (to include at minimum: amphetamines, barbiturates, cocaine, opiates, cannabinoids and benzodiazepines) 				

Abbreviations: ALT (SGPT) = alanine aminotransferase (serum glutamic pyruvic transaminase); AST (SGOT) = aspartate aminotransferase (serum glutamic oxaloacetic transaminase); BUN = blood urea nitrogen; FSH = follicle stimulating hormone; HBsAg = hepatitis B surface antigen; anti-HBc = hepatitis B core antibody; hsCRP = highly sensitive C-reactive protein; MCH = mean corpuscular haemoglobin; MCV = mean corpuscular volume; RBC = red blood cell; UACR = urinary albumin-creatinine ratio; WBC = white blood cell, pH= hydrogen ion concentration.

1. The following post-dose results will be blinded to Investigators and blinded Sponsor representatives: total WBCs; absolute and percentage eosinophils; and percentage neutrophils, lymphocytes, monocytes and basophils.

All laboratory tests with values that are considered clinically significantly abnormal during participation in the study or within the defined in clinic follow up periods should be repeated until the values return to normal or baseline. If such values do not return to normal within a period judged reasonable by the investigator, the etiology should be identified and the sponsor notified.

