4. STUDY DESIGN

4.1. Overall Design

This is a single ascending dose FTIH study to evaluate the safety, tolerability, immunogenicity, pharmacokinetics and pharmacodynamics of subcutaneously administered GSK3511294 in participants with mild to moderate asthma and blood eosinophils \geq 200 cells/ μ L.

This study is a multi-center, randomised, double-blind (sponsor clinical pharmacology modelling and simulation [CPMS] and statistician representatives open), placebo-controlled, parallel-group study. Each participant will receive a single dose of GSK3511294 or placebo, as shown in [Figure 2](#).

Figure 2 Summary of GSK3511294 first-time-in-human study design

Notes: Planned single ascending SC doses of GSK3511294 are 2, 10, 30, 100 and 300 mg. Actual dose levels beyond the 2 mg starting dose will be confirmed based on the emerging data. Planned cohort sizes are shown; additional participants may be added to cohorts, if necessary to characterise the pharmacokinetics or pharmacodynamics of GSK3511294. In each cohort, participants will be randomised 3:1 to receive GSK3511294 or placebo. Additional cohorts of up to 12 participants may be added to test additional dose levels or to repeat a dose level already tested, if deemed necessary; however, the dose will not exceed 300 mg. The planned sample size is n=48 participants; the maximum sample size is n=72 participants (excluding replacements for prematurely withdrawn participants).

- Sentinel participants: In each cohort, one placebo and one GSK3511294 participant will be dosed before the remaining participants. Providing no safety issues are identified in the sentinel participants over an observation period of at least 72 hours,

the remaining participants in the cohort may be dosed. The Investigator will discuss any safety concerns with the GlaxoSmithKline (GSK) medical monitor before dosing the remaining participants in a cohort. Sentinel dosing is not required in cohorts investigating a dose lower than or equal to the highest dose tested to date.

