4.3. Dose Escalation

- The Dose Escalation Committee (DEC) will consist of the Principal Investigator(s) (or appropriate designee), GSK Medical Monitors, GSK Study Team Leader, GSK Clinical Pharmacology Modelling and Simulation (CPMS) representative, a GSK Global Clinical Safety and Pharmacovigilance (GCSP) representative and GSK Statistician representative. The GSK CPMS and statistician representatives will remain unblinded throughout the course of the study.
- The DEC will select and approve doses throughout the study, and will review available data from all participants in each cohort before initiating each new dose level. Dose escalation may occur only after review of the following data at the highest dose level tested to date: at least 4 weeks' post-dose safety data and at least 2 weeks' post-dose PK data from at least 4 participants on active treatment; and at least 72 hours' post-dose safety data from the remaining participants in the cohort. In the unlikely event that one or more of the remaining participants discontinued the study within 72 hours after dosing, all available safety data from that/those participants will be reviewed.
- Owing to the mechanism of action of GSK3511294, blood eosinophil results have the potential to unblind. Therefore, study personnel will be blinded to post-dose blood eosinophil results for individual participants. The sponsor CPMS and statistician representatives will review individual data, but summary statistics for the active group only will be provided to the remaining members of the DEC for the purposes of dose selection. Similarly, to minimise the risk of unblinding during DEC meetings, no individual PK data will be discussed; summary statistics only will be provided to blinded members of the DEC. If ongoing analyses are based on an incomplete cohort, to avoid unblinding, the DEC (except the GSK CPMS and statistician representatives) will be blinded to the number of participants included in the summaries of PK and blood eosinophils for that cohort.
- This protocol allows some alteration from the currently outlined dosing schedule, but the maximum single dose will not exceed 300 mg.
- The dose will be increased only if safety and tolerability at previous dose levels are acceptable, and also if the predicted exposure (upper 95% prediction interval for C_{max} and AUC) at the next dose level does not exceed the mean exposure observed at the NOAEL in monkey in the 26 week toxicity study (100 mg/kg).

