7.1. Time and Events Table

Procedure	Pre-Screen 1	Screen 2	In-Patient Period ^{3,4}							Out-patient Visits ^{4,5}													
			Day -1	Day 1			Day 2	Day 3	Day 4	Week													
				Pre-dose	0	2 h	8 h	24 h	48 h	72 h	NA	1	2	4	8	12	18	24	26	32 ⁵	36 ⁵	40 ⁵	
				5	8	15	29	57	85	127	169	183	225 ⁵	253 ⁵	281 ⁵	Day							
Haematology (including blood eosinophil count), Clin. Chem., Urinalysis and hsCRP		X	X					X	X	X	X	X	X	X	X	X	X	X	X	X	X	X	
Serum save (for immunological analysis, if needed)		X																					
Inflammatory markers		X																					
Complement (C3 & C4)		X	X					X	X	X	X	X	X	X	X	X	X	X	X	X	X	X	
Total IgE			X					X	X	X	X		X	X	X	X	X	X	X	X	X	X	
PK Blood Samples																							
Immunogenicity				X									X	X	X	X	X	X	X	X	X	X	
CICs				X				X					X	X	X	X	X	X	X	X	X	X	
12-lead ECG ¹⁴		X	X	X		X	X	X	X	X	X	X	X	X	X	X	X	X	X	X	X	X	
Vital signs ¹⁵		X	X	X		X	X	X	X	X	X	X	X	X	X	X	X	X	X	X	X	X	
AE/SAE review (inc local ISR up to 72 h after dosing)				X	¹⁶																		
IL-5 sample			X										X	X		X	X	X	X	X	X	X	
Exploratory biomarkers of asthma in blood			X												X			X					
Spirometry		X	X			X		X		X		X		X		X				X	X	X	
PEF Training ¹⁷		X																					
PEF ¹⁷													X	¹⁷									
Diary review ¹⁷													X	X	X	X	X	X	X	X	X	X	

Abbreviations: ACT = Asthma Control Test; AE = adverse event; BMI = body mass index; CICs = circulating immune complexes; CRP = C-reactive protein; ECG = electrocardiogram; FSH = follicle stimulating hormone; h = hour(s); Hep B = Hepatitis B; Hep C = Hepatitis C; HIV = human immunodeficiency virus; IgE = immunoglobulin E; IL-5 = interleukin-5; IP = Investigational Product; ISR = injection site reactions; PEF = peak expiratory flow; PK = pharmacokinetic; SABA = short acting β -agonist; SAE = serious adverse event.

Notes:

1. Pre-screen up to 12 weeks before dosing. Blood eosinophils must be ≥ 200 cells/ μ L for participants to proceed to screening. Blood eosinophil count may be existing data or obtained at a pre-screen visit.
2. Screening up to 4 weeks before randomisation. Screening procedures may be done at one or more visits, within the screening window.
3. In the UK, all participants will be in-patient for at least 72 h after dosing. In Germany, all participants will be in-patient for at least 8 days after dosing (see [Appendix 8](#) for the German-specific time and events table).
4. Allowed time deviations will be documented in the Study Reference Manual.

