12.2. Appendix 2: Liver Safety Required Actions and Follow up Assessments

Liver chemistry increased monitoring criteria and required follow up assessments

Liver Chemistry Increased Monitoring Criteria	
Required Actions and Follow up Assessments following Liver Event	
Actions	Follow Up Assessments

ALT-absolute
 
ALT\geq3xULN
 
If ALT\geq3xULN AND bilirubin^{1,2} \geq 2xULN (>35% direct bilirubin) or INR >1.5, Report as an SAE.
 
See additional Actions and Follow Up Assessments listed below
	
 Report the event to GSK within 24 hours Complete the liver event CRF, and complete an SAE data collection tool if the event also meets the criteria for an SAE² Perform liver event follow up assessments Monitor the participant until liver chemistries resolve, stabilise, or return to within baseline (see MONITORING below) 
 Viral hepatitis serology³ Obtain INR and recheck with each liver chemistry assessment until the transaminases values show downward trend Obtain blood sample for pharmacokinetic (PK) analysis, obtained within a week of meeting increased liver monitoring criteria⁴ Serum creatine phosphokinase (CPK) and lactate dehydrogenase (LDH). Fractionate bilirubin, if total bilirubin\geq2xULN Obtain complete blood count with differential to assess eosinophilia Note: The mechanism of action of GSK3511294 leads to lowering of eosinophils. Investigators should be blinded to those results, unless unblinding is required for participant safety. Record the appearance or worsening of clinical symptoms of liver injury, or hypersensitivity, on the AE report form Record use of concomitant medications on the concomitant medications report form including

	
acetaminophen, herbal remedies, other over the counter medications.
 
 Record alcohol use on the liver event alcohol intake case report form

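### Does the Section 7.3.6 note on local laboratory results open a route to unblinding through post-dose eosinophil counts?

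*Protocol*

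**What the plan says.** The note in Section 7.3.6 makes local results necessary only when central results will not arrive in time for a treatment or response evaluation. Its post-dose examples include "at 48 h post-dose for all sentinel participants; at 48 h post-dose when results should be available before the participant is discharged" in the UK, Day 8 before discharge in Germany, and any time a participant is unwell. It adds that "If a local sample is required it is important that the sample for central analysis is obtained at the same time" and, as to recording, that "if the local laboratory results are used to make either a treatment or response evaluation, the results must be entered into the CRF".

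The scheduled safety panel at these visits is one row of the Time and Events Table (Section 7.1): "Haematology (including blood eosinophil count), Clin. Chem., Urinalysis and hsCRP".

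The blinding rule appears in two places. Footnote 1 to Table 5, also in Section 7.3.6, reads "The following post-dose results will be blinded to Investigators and blinded Sponsor representatives: total WBCs; absolute and percentage eosinophils" and goes on to list the percentages of neutrophils, lymphocytes, monocytes and basophils. The white-cell heading in Table 5 points to that footnote. Section 4.3 says that "study personnel will be blinded to post-dose blood eosinophil results for individual participants". Appendix 2, which asks for a blood count after a liver event, adds its own reminder: "Investigators should be blinded to those results, unless unblinding is required for participant safety".

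**The concern.** A local report goes straight back to the site, without passing through a central vendor that can suppress lines. The note mentions neither blinding nor footnote 1, and its recording duty is unqualified. A site that took the sentence literally could believe it had to read the full local haematology report and copy it into the CRF. Masking the eosinophil line alone would not help, because footnote 1 leaves the absolute counts of the other four cell types open and a local total white-cell count would then give eosinophils by subtraction. Amendment 4 introduced the footnote to close that gap.

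The primary endpoint is safety, investigators judge causality, and most halting criteria in Section 5.5 depend on an event being at least possibly drug-related. In each cohort "one placebo and one GSK3511294 participant will be dosed before the remaining participants", so learning the treatment of one sentinel reveals that of the other, just before the rest of the cohort is dosed. The unwell-participant trigger would bring in local results at the moment when causality is being judged.

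**Working it through.** The protocol states no figure on this point, so the check is mainly one of text. The arithmetic only bounds what a breach would reveal.

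**1. Does the blinding rule reach local results?** Footnote 1 is defined by analyte, time (post-dose) and audience (investigators and blinded sponsor staff). Section 4.3 is defined by analyte, time and study personnel. Neither mentions which laboratory produced the result, so both cover local results.

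**2. Does the recording duty conflict with it?** The duty is conditional on use in an evaluation. A blinded investigator cannot use a value that footnote 1 withholds. The duty therefore falls on the open results: chemistry, platelets, red-cell indices, urinalysis, hsCRP and the absolute counts of the other white cells. A site can obey both rules at once. The note lists no local analytes and nowhere requires a local differential to be reported. The paired central sample preserves the eosinophil data.

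**3. Does subtraction work if footnote 1 is followed?** Eosinophils = total WBC − (neutrophils + lymphocytes + monocytes + basophils). With illustrative values, 6.00 − (3.50 + 1.80 + 0.40 + 0.05) = 0.25 ×10⁹/L. This needs the total, which is blinded. The total could also be recovered from one percentage and its absolute count (3.50 / 0.583 = 6.00), but the percentages are blinded too. With the footnote applied, only the sum of the four open counts (5.75) is known, and eosinophils cannot be derived from it.

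**4. Who could be affected?** There are 5 planned cohorts with 2 sentinels each: 5 × 2 = 10, and 10/48 = 20.8%. The other 48 − 10 = 38 have local results only if central ones are late. In the operative wording the sentinel item is also an example under that condition. Only the Amendment 5 rationale describes it as required for all sentinels.

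**5. What would a breach reveal in a sentinel pair at 48 h?** Call the participant with the lower ratio to baseline the active one. With reduction r on active, no change on placebo, and SD s of each person's log ratio, the probability of being right is Φ(−ln(1 − r) / (s√2)). The protocol gives neither r at 48 h nor s, so both are assumptions.

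| Assumed reduction r | s = 0.3 | s = 0.5 | s = 0.7 |
|---|---|---|---|
| 10% | 0.60 | 0.56 | 0.54 |
| 25% | 0.75 | 0.66 | 0.61 |
| 50% | 0.95 | 0.84 | 0.76 |

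For example, at r = 25% and s = 0.5: 0.2877 / 0.7071 = 0.407, and Φ(0.407) = 0.66. Chance is 0.50. The range runs from near chance to near certainty, so it does not settle how large the leak would be.

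**The case for a change.** The best case for a change is practical. Local reports are ordered, received and transcribed by the people who must stay blind, so a rule without a mechanism is easier to break there than with central results. Amendment 5 widened the local-laboratory occasions after Amendment 4 had tightened the blinding, and did not restate it. Appendix 2 shows that the sponsor does repeat the instruction elsewhere. An early effect is also plausible: Section 2.2 gives a circulating eosinophil half-life of 8 to 18 hours and expects a rapid fall. By Day 8 the fall should be larger, since Section 4.6 predicts the maximum at 2 mg, about 75%, at roughly two weeks.

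Part of this stands. The note lacks a cross-reference, and one would do no harm. But the argument concerns how sites carry out a rule that is already stated and unqualified. Section 7.3.6 sends laboratory conduct to the Laboratory Manual and sample handling to the Study Reference Manual, neither of which is at hand, and masking of local reports is the kind of detail they hold. The reminder in Appendix 2 is natural because the count there is ordered specifically to look at eosinophils. It does not imply that the general rule lapses elsewhere.

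**Conclusion.** No change to the plan follows. The note is silent on blinding but not at odds with it, and a site that follows all of Section 7.3.6 together with Section 4.3 keeps every listed analyte blinded, whichever laboratory measures it. An added sentence would mainly repeat a rule already given twice.

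Exposure would require a site to breach footnote 1, and would arise only where local results are obtained. The consequence is also limited: safety is summarised descriptively with no formal comparisons (Sections 9.1 and 9.4.1), and the rest of a cohort is dosed if the sentinels show no safety issue, not on a contrast between the two. The conclusion rests on reading footnote 1 as written, covering local as well as central results, and on the operational manuals giving sites a way to apply it.
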